14.4. Type I error rate

The Type I error rate is 5% and all tests are two-tailed.

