14.5.4. Power

The assumptions underlying the power analysis for MET-weighted minutes of MVPA are summarized in Table 14.1.

- The mean and standard deviation for MET-weighted minutes of MVPA are taken from the variance components substudy of 8th grade girls (n=426) selected to represent 12 schools from the six Field Centers. Both are based on a cutpoint of 1500 CSA counts per half-minute to define MVPA, a figure drawn from the findings of the CSA calibration substudy.
- As noted above, the Type I error rate for the primary analysis is 5% and twotailed.
- Given 60 girls per school invited to the baseline survey, we conservatively
 estimate the overtime correlation among schools at zero (the correlation among
 measures taken on the same schools two years apart). We make no provision
 for overtime correlation among the girls (the correlation among measures taken
 on the same girls two years apart), due to our plan to ignore any overlap in the
 6th and 8th grade samples.
- We plan to randomize 18 schools to each of two conditions.
- We assume each Field Center will average 60 girls per school selected for invitation to the baseline survey and 120 girls per school selected for invitation to the follow-up survey. Schools with fewer girls available for CSA measurements may participate in TAAG so long as there is a minimum of 90 girls who are eligible to be selected for invitation to each survey and so long as each Field Center averages 60 girls per school at the baseline survey and 120 girls per school at the follow-up survey.
- We anticipate that girls enrolled in the intervention schools during 7th and 8th grade will display an intervention effect of 15.6 more MET-weighted minutes of MVPA than their counterparts in the control schools; this effect is equivalent to 10% of the mean MET-weighted minutes of MVPA and to a 50% reduction in the decline anticipated between the 6th and 8th grades. We anticipate that girls enrolled in the intervention schools only in the 8th grade will display an intervention effect of 9.4 more MET-weighted minutes of MVPA and to a 30% reduction in the decline anticipated between the 6th and 8th grade soft MVPA, this effect is equivalent to 6% of the mean MET-weighted minutes of MVPA and to a 30% reduction in the decline anticipated between the 6th and 8th grades.
- Our eligibility criteria are designed to limit the two-year attrition to 36%.

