- Based on our experience in the variance components substudy, we anticipate a refusal rate for CSA measurements at 8th grade of no more than 20%.
- Also based on that experience, we assume six 24-hour days of CSA observation
 per girl, with girls measured in approximately equally sized weekly groups over a
 period of three weeks in each school. This can be accomplished by taking the
 monitors off of the girls on the same day of the week on which they were put on.
 Analysis of the variance components substudy data indicated that reducing the
 number of days from seven to six has little effect on any of the estimated
 parameters. If that plan is adopted, the data suggest that Monday is the

preferred day to avoid, because there was lower compliance than on other days.

- The power calculations assume that occasional missing CSA data within a girl's 7-day records are replaced via imputation based on the EM algorithm; details are provided in the Appendix to Chapter 14.
- The power calculations ignore refusals. Refusals that are unrelated to study condition or physical activity level will not bias the estimate of the intervention effect. We anticipate that no more than 25% of the refusals are non-ignorable. Separate analyses suggest that power declines by about 3% if we impute values for 25% of the refusals, assuming no intervention effect for those cases. At the same time, the intervention effect is overestimated by only about 5% if those refusals are ignored. Given this minor adverse effect in terms of bias, we do not believe it is necessary to impute for refusals in the primary analysis. We propose imputation for refusals in a secondary analysis.

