- The observed value of the school-level ICC for MET-weighted minutes of MVPA is 0.000, based on an analysis of the variance components substudy data consistent with that proposed above for the primary analysis. We view that estimate as optimistic and prefer to be cautious, given that we had a small sample of schools in the variance components substudy, thereby limiting the precision of our estimate. Separate analyses suggest a 50% probability that the true value is below 0.003 given an observed value of 0.000, and so we propose 0.003 as our realistic estimate of this Intraclass Correlation. Prior experience with Intraclass Correlations in other school based studies suggests a value of 0.01 as a conservative estimate, and we note that there is a 62% probability that the true value is below 0.01 given an observed value of 0.000. With these considerations in mind, we used these three values to perform the power analyses summarized in Table 14.2.

Table 14.1. Assumptions Underlying the Power Analysisfor MET-Weighted Minutes of MVPA

Mean MET-weighted minutes of MVPA, based on 1500	156.4 MET minutes
cpm	
SD MET-weighted minutes of MVPA, based on 1500	94.9
cpm	
Two-tailed Type I Error Rate	5%
Over-time correlation among schools	none
Over-time correlation among girls	none
Schools per condition	18
Girls per school selected for CSA measurement at	Average 120, Minimum 90
posttest	
Intervention effect	
for girls enrolled in intervention schools in 7 th and 8 th	15.6 MET min (10% of
grade	mean)
for girls enrolled in intervention schools only in 8 th	9.4 MET min (6% of mean)
grade	
Attrition rate over two years	36%
Refusal rate at follow-up for CSA measurements	20%
CSA measurement schedule	
days per girl	6 24-hour days
weeks per school	3
Imputation of occasionally missing CSA data	EM algorithm
Imputation for non-ignorable refusals	none
School-level Intraclass Correlation	
observed estimate	0.000
realistic estimate	0.003
conservative estimate	0.010

Tables 14.2 summarizes power for TAAG based on these assumptions. These results indicate that even if the Intraclass Correlation is as high as 0.01, if we invite 120 girls from each school to participate in the follow-up survey, and no more than 20% of that sample refuse to provide CSA data, we have 89% power for the projected intervention effect, given the assumptions noted in Table 1.

ICC	Girls/Sc	hool Invite	d to Partic	cipate at F	ollow-up
100	90	105	120	135	150
0.010	81%	85%	87%	89%	90%
0.003	92%	95%	97%	98%	98%

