Appendix 4: Data Analysis

A.4.1. Statistical model

For the primary analysis of MET-weighted minutes of MVPA, the data are analyzed in two stages and as though there is no overlap among girls measured in the 6th and 8th grade cross-sectional samples. This two-stage approach serves two useful functions. First, it avoids many of the complexities inherent in a single-stage mixed-model regression analysis of data from a multi-center group-randomized trial (Murray, 1998b). Second, it mimics an analysis of covariance performed on 8th grade data, with regression adjustment for 6th grade values on the primary endpoint.

In the first stage, we regress the girl's MET-weighted minutes of MVPA on school, time (baseline or follow-up), their interaction, ethnicity and week of data collection; study condition is not included in that model:

$$MVPA = school + time + time \times school + ethnicity + week + error$$
(1)

Here, all terms are modeled as fixed effects, except for week and residual error. Of interest in this first stage is the estimation of ethnicity-adjusted school means for MET-weighted minutes of MVPA, estimated for each school at 6th grade and at 8th grade. We include ethnicity in Eq. 1 because we observed a substantial reduction in the school-level intraclass correlation (ICC) in the variance components substudy when we adjusted for ethnicity. We include week as a random effect because we observed a substantial reduction in the same ICC in the baseline survey when we included week as a random effect. Given that the intraclass correlation is so strongly related to power, we want to take every opportunity to make it as small as possible. We adjust for ethnicity in a pooled analysis of 6th and 8th grade data, rather than in separate analyses, so as to standardize the results for the two surveys against the same reference distribution, here the average ethnicity distribution over time.

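### The ICC of 0.010 is presented as a conservative case, but the only probability the protocol gives leaves a 38% chance that the true ICC is higher, and Table 14.2 shows no power beyond it

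*Protocol*

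**What the plan says.** Section 14.5.4 uses three values for the school-level ICC of MET-weighted minutes of MVPA:

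- 0.000, the value observed in a substudy of 426 girls from 12 schools, which the protocol itself calls optimistic because so few schools were sampled;
- 0.003, called realistic, with a 50% probability that the true value is lower;
- 0.010, where experience in other school-based studies "suggests a value of 0.01 as a conservative estimate". The bullet then adds: "we note that there is a 62% probability that the true value is below 0.01 given an observed value of 0.000".

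The conclusion drawn from Table 14.2 opens: "These results indicate that even if the Intraclass Correlation is as high as 0.01", and goes on to give 89% power with 120 girls invited per school and 20% refusing. The table's cell for that case (ICC 0.010, 120 invited) reads 87%; 89% stands in the 135 column. Appendix A.4.6.1 repeats 89% for the 120-girl case. Table 14.2 has no ICC row above 0.010, and its lowest printed power is 81%.

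Appendix A.4.1 gives this reason for having a week term in the first-stage model: "because we observed a substantial reduction in the same ICC in the baseline survey when we included week as a random effect". A school-level ICC has therefore been computed on the trial's own baseline data. Its value is not given, and section 14.5.4 does not use it.

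**The concern.** A value with a 38% chance of being exceeded, on the only probability offered, does not mark the unfavourable end of the range. The wording still invites that reading: the value is labelled conservative, it is introduced with an even-if clause, and the table stops there. A reader would take power in the high eighties as what remains when the ICC turns out badly.

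This matters because the ICC strongly drives power in a 36-school trial, as Appendix A.4.1 says itself. If the unfavourable case is understated, a null result is more easily read as good evidence of no effect than the design warrants.

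**Working it through.** **Inputs from the protocol**

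- Alpha (section 14.4): "The Type I error rate is 5% and all tests are two-tailed".
- Schools (section 14.5.4): "We plan to randomize 18 schools to each of two conditions".
- Girls (section 14.5.4): an average of "120 girls per school selected for invitation to the follow-up survey".
- Refusal (section 14.5.4): "we anticipate a refusal rate for CSA measurements at 8th grade of no more than 20"%. So m = 0.8 × 120 = 96 girls measured per school.
- SD 94.9 (Table 14.1).
- Error degrees of freedom 28 (Appendix A.4.1).
- Effects of 15.6 MET-minutes (girls exposed in 7th and 8th grade) and 9.4 (8th grade only) (Table 14.1).

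**Assumption.** The protocol does not state how the two effects are combined. An 80/20 blend is used, consistent with 20% attrition a year (0.8 × 0.8 = 0.64, the stated 36% over two years):

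0.8 × 15.6 + 0.2 × 9.4 = 12.48 + 1.88 = 14.36 MET-minutes.

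**Step 1: reproduce Table 14.2**

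SE = SD × √[2 × (1 + (m − 1) × ICC) / (m × 18)], with a two-sided noncentral t test on 28 df.

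At ICC 0.010 and 120 invited:
- design effect = 1 + 95 × 0.010 = 1.95
- SE = 94.9 × √(2 × 1.95 / 1,728) = 4.51
- effect/SE = 14.36 / 4.51 = 3.19
- power = 86.7%, against 87% printed.

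All 15 cells of Table 14.2 reproduce within 0.7 percentage points. A 64/36 blend (13.37 MET-minutes) does not fit: it gives 81.6% in this cell. The 89% in the text matches a normal approximation to the same case (89.0%).

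**Step 2: the probability of exceeding 0.010**

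From the stated figure: 1 − 0.62 = 0.38. No modelling is needed.

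The 62% is consistent with the substudy's size. Take an F pivot with observed F = 1, 426/12 = 35.5 girls per school, 12 − 6 = 6 school df and 414 error df. Then:

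P(ICC < r) = P(F(6, 414) > 1 / [1 + 35.5 × r/(1 − r)])

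This gives 49.2% at r = 0.003 and 62.1% at r = 0.010, against the printed 50% and 62%. With 11 school df it gives 54% and 70%, which does not fit. The 6 df and F = 1 are inferred from this agreement; the protocol does not state them.

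**Step 3: power beyond the table's last row (120 invited, same inputs)**

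| ICC | Power |
|---|---|
| 0.003 | 97% |
| 0.010 | 87% |
| 0.015 | 79% |
| 0.020 | 71% |
| 0.030 | 59% |
| 0.050 | 43% |

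Power passes below 80% at an ICC of about 0.014.

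**Step 4: how likely such ICCs are (approximate only)**

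Extending the Step 2 pivot puts the 80% and 90% upper limits at about 0.026 and 0.046, and the chance of an ICC above 0.014 at roughly one in three. These limits are sensitive to the inferred F. At F = 0.8 they become 0.016 and 0.032; at F = 0.6 they become 0.005 and 0.018.

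**The case against.** The best defence is that nothing is hidden or miscalculated in the ICC bullet. The 62% is printed in the same sentence as the label, the even-if clause is literally a conditional statement, and 0.010 is never called an upper confidence limit. The label also rests on outside school-based studies, not on the substudy, and combining the two sources could bring the 38% down. That is fair as far as it goes. But the outside experience is given without data, so the protocol offers no figure that would make 0.010 conservative, and the one figure it does offer does not.

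Other points on that side stand:

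- A reader might infer that 0.010 is a middle case. It is not: the protocol's median is 0.003 with 97% power, and 0.010 is more than three times that.
- A reader might infer a firm probability of about one in three that power is under 80%. The protocol does not support a firm figure. It depends on an inferred substudy model, on an observed F of exactly 1 (an ICC reported as 0.000 may be an estimate truncated at zero), and on treating confidence levels as a probability distribution.
- A reader might infer that the baseline survey shows 0.010 to be too low. No baseline value is given, and what Appendix A.4.1 reports is a reduction in the ICC once week is modelled.
- The final test uses the observed between-school variance on 28 df, so the type I error rate and the eventual confidence interval do not depend on the planning ICC.

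The over-time school correlation is also set cautiously at zero. Appendix A.4.6.1 sizes the related loss at about one point (90% to 89%), which is small beside the fall from 87% to 71% between ICC 0.010 and 0.020.

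**Conclusion.** The point holds as one about how power is presented. An ICC of 0.010 is an above-median planning value, at about the 62nd percentile on the substudy evidence, and the power quoted there is not an unfavourable-case figure. Doubling the ICC to 0.020 costs about 16 points of power (87% to 71%), and Table 14.2 shows nothing of this. Separately, the text's 89% disagrees with the table's 87% for the same case.

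The 38% follows directly from the protocol's 62% and reflects the 12-school substudy alone. The power values at given ICCs rest on the assumed 80/20 effect blend, which is supported by its reproducing every cell of Table 14.2. The likelihood of ICCs well above 0.010 is only approximate. None of this shows that the trial is underpowered; it shows that the protocol has not established the bound its wording implies.

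**What to change.** In section 14.5.4:

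1. Stop presenting 0.010 as a conservative bound. Describe it as an above-median value with a stated 38% chance of being exceeded on the substudy evidence, or quantify the outside experience that justifies the label.
2. Add rows for ICC 0.02, 0.03 and 0.05 to Table 14.2.
3. Correct the text's 89% to the table's 87% for 120 girls invited, and reconcile the same figure in Appendix A.4.6.1.
4. Report the school-level ICC from the baseline survey with its upper confidence limit, and the power at both, whichever way that moves the statement.

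The cost is a few table rows, a few sentences and one calculation on data already collected. The stated power becomes less favourable at the added ICC values. Sample size, design and analysis do not change.

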The primary analysis requires 72 time x school means from the first stage, to be used in a second stage analysis for intervention effects. This is unaffected by changing the size of the baseline sample, except that the baseline means are estimated with fewer observations than the follow-up means. The role of the baseline mean in the primary analysis is as a covariate, and to the extent that we increase variation in those means by reducing the number of observations contributing to each mean, we may reduce the over time correlation at the school level, and so reduce power. However, that reduction in power cannot be large: even if the over time correlation were reduced to zero, the loss of power is minimal, so that given 120 girls per school invited to participate and an intraclass correlation of 0.01, the power drops from 90% with 120 girls per school invited at baseline to 89% with 60 girls per school invited at baseline. This is reflected in the power analysis presented for the primary analysis in Section 14.

A.4.6.2. Implications for Secondary Analyses

Any secondary analysis employing the same analysis plan as proposed for the primary analysis is negligibly affected by reducing the size of the baseline survey sample, for the reasons noted above. The two secondary analyses that are proposed that employ a different analysis plan are those involving cohort analyses for mediation and for effect modification. Those analyses are adversely affected by reducing the size of the baseline sample, as that necessarily reduces the size of the cohort available for those analyses.

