Under the original plan, we expected to have 49 girls per school available in the cohort if we selected 120 girls per school at baseline given a two-year attrition rate of 36% and annual refusal rates of 20%. That figure is reduced to 25 girls per school given only 60 girls per school at baseline. With 36 schools, that still provides 900 girls in the cohort, and the degrees of freedom for those analyses are unchanged, as they are still based on 36 schools. Power calculations for an intervention effect on a hypothesized mediator indicate that there is 80% power for an effect of 0.21 sd units and 90% power available for an effect of 0.25 sd units. An effect size of 0.25 sd units is widely considered to be small (Cohen, 1988). In contrast, our hypothesized intervention effect on MET-weighted minutes of MVPA of 10% represents an effect size of 14.5/86=0.17 sd units, which is quite small. This is why, the power for the mediation analysis is reasonable even with a reduced baseline sample.

Power for moderation is diminished by reducing the size of the baseline sample, but is already poor, so we don't do too much harm by reducing it further.

A.4.7. Power Calculations for PWC₁₇₀

Cardiovascular fitness will be assessed by the Physical Work Capacity 170 (PWC₁₇₀) cycle ergometer test. For the PWC₁₇₀ test, the outcome measure will be the predicted power output based on a two-stage required to elicit a heart rate of 170 beats/min. We will express, PWC₁₇₀ as kilogram-meters per minute per kilogram lean body weight (kg-m/min/kg). The estimates used in the power calculations below were from studies that controlled for total weight, rather than more precise measures of lean body weight that we will use. Therefore, the estimates shown here may be conservative.

Using a cross-sectional design, we will model the 36 school-level fitness means at the end of 8th grade as a function of treatment condition, site, and school. Power calculations were performed for a 2-sided type I error rate of 0.05. We assumed a mean and standard deviation for PWC₁₇₀ of 11 ± 2.7, an ICC estimate of 0.01. The following table shows the power to detect a 5% or 6% difference in fitness at 8th grade as a function of the number of girls invited to participate in the fitness measure in each school, with the expectation that 80% will participate.

POWER FOR PWC ₁₇₀ - 36 Schools				
Girls Invited	Intervention effect			
Per School	5% 6%			
60	0.88	0.96		
50	0.84	0.94		
40	0.78	0.91		
30	0.68	0.83		

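### Section 14.5.4 states 89% power where its own Table 14.2 gives 87%, and Appendix 4 and a Table 14.1 label carry related mismatches

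*Protocol*

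**What the plan says.** Section 14.5.4 lists the planning assumptions and collects them in Table 14.1: mean 156.4 and SD 94.9 MET-minutes, 18 schools per condition, 20% refusal, no over-time correlation, and school-level ICCs of 0.000, 0.003 and 0.010. Two effects are posited. Girls enrolled in 7th and 8th grade "will display an intervention effect of 15.6 more MET-weighted minutes of MVPA"; girls enrolled only in 8th grade show "an intervention effect of 9.4 more MET-weighted minutes of MVPA".

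The ICC 0.010 row of Table 14.2 reads 81%, 85%, 87%, 89% and 90% for 90, 105, 120, 135 and 150 girls invited. The sentence introducing that table says that, at this ICC with 120 invited and no more than 20% refusing, "we have 89% power for the projected intervention effect, given the assumptions noted in Table 1".

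Two places in Appendix 4 bear on the same figures. A.4.6.1, on the smaller baseline sample, says "the power drops from 90% with 120 girls per school invited at baseline to 89% with 60 girls per school invited at baseline" and adds that Section 14 reflects this. A.4.6.2 says that the hypothesized 10% effect "represents an effect size of 14.5/86=0.17 sd units, which is quite small".

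On the threshold behind the mean and SD, the text of 14.5.4 says "Both are based on a cutpoint of 1500 CSA counts per half-minute to define MVPA", as section 9.2.1 does, while the corresponding rows of Table 14.1 are labelled 1500 cpm.

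**The concern.** The sentence and the table describe the same design point and differ by 2 percentage points, so a reader who quotes the primary power from the text quotes a figure that the table refutes. The pointer is also wrong: the assumptions stand in Table 14.1, whereas the only Table 1 in the protocol is the power table for girl-level effect modification in Appendix 4.

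The appendix repeats the 89% and describes the primary effect with a different difference and SD. That leaves two sets of planning figures for one endpoint. The cpm label, read as counts per minute, would halve the threshold that defines that endpoint.

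**Working it through.** **Inputs from the Protocol**

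- Two-sided alpha 5%: "the Type I error rate for the primary analysis is 5% and twotailed".
- 18 schools per arm: "We plan to randomize 18 schools to each of two conditions".
- SD 94.9, ICC 0.01, 20% refusal and zero over-time correlation (Table 14.1).
- 28 error degrees of freedom (Appendix A.4.1).
- Girls measured per school: m = 0.8 × 120 = 96.

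**Assumed input: the weighting of the two effects.** The Protocol does not say how 15.6 and 9.4 are combined. Two-year attrition of 36% equals 1 − 0.80², or 20% a year if constant. Taking 20% of 8th graders at the partial effect gives

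δ = 0.8 × 15.6 + 0.2 × 9.4 = 14.36 MET-minutes.

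**Formulae**

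- SE = √[2 × SD² × (1 + (m − 1) × ICC) / (m × 18)]
- Power = T₂₈(δ/SE − t₀.₉₇₅,₂₈), where T₂₈ is the t distribution function with 28 df and t₀.₉₇₅,₂₈ = 2.048

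**The disputed case (ICC 0.01, 120 invited)**

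- SE = √[2 × 94.9² × 1.95 / (96 × 18)] = 4.51
- δ/SE = 14.36 / 4.51 = 3.18
- Power = T₂₈(3.185 − 2.048) = 86.7%

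**All of Table 14.2 with δ = 14.36**

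| ICC | Source | 90 | 105 | 120 | 135 | 150 |
|---|---|---|---|---|---|---|
| 0.010 | stated | 81 | 85 | 87 | 89 | 90 |
| | recomputed | 81.1 | 84.3 | 86.7 | 88.6 | 90.0 |
| 0.003 | stated | 92 | 95 | 97 | 98 | 98 |
| | recomputed | 92.1 | 94.7 | 96.4 | 97.5 | 98.3 |
| 0.000 | stated | 96 | 98 | 99 | 99 | 100 |
| | recomputed | 95.9 | 97.8 | 98.8 | 99.4 | 99.7 |

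All 15 cells agree within 1 point, so the table is consistent with the stated inputs and the sentence is the outlier. Reaching 89% at ICC 0.01 would take about 111 girls measured per school (111/0.8, or about 139 invited). With 120 invited it would take an ICC of about 0.0086.

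**Sensitivity to the weighting (same cell)**

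- 64/36 blend: δ = 0.64 × 15.6 + 0.36 × 9.4 = 13.37, power 81.6%
- 80/20 blend: δ = 14.36, power 86.7%
- No dilution: δ = 15.6, power 91.5%

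**Effect size**

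- Appendix A.4.6.2: 14.5/86 = 0.169 SD. If 14.5 is 10% of the mean, the implied mean is 145.
- Table 14.1: 15.6/94.9 = 0.164 SD, with a mean of 156.4.

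**Threshold.** 1500 counts per half-minute is 3000 counts per minute. A literal 1500 counts per minute would be half of that.

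**The case against.** A normal approximation with the Table 14.1 inputs and δ = 14.36 gives 89.0% at 120 invited, so the sentence could be a large-sample figure. This does not rescue it. The approximation ignores the 28 df of the planned test, and its row (83.8, 86.8, 89.0, 90.6, 91.9) does not match Table 14.2, which the sentence claims to summarize.

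A reader might infer more than the documents support, in four ways:

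- **That the power inputs themselves are wrong.** They are not: the numbers in Table 14.1 reproduce the whole of Table 14.2.
- **That 14.5/86 is an older set of inputs from which the 89% was left over.** No section dates those values. With SD 86 and an 80/20 blend of 10% and 6% of 145 (δ = 13.34), power is 88.3%. That is compatible with a leftover figure, but the normal approximation explains 89% at least as well.
- **That the case for 60 girls per school at baseline collapses.** A.4.6.1 argues that the loss from a smaller baseline sample is small. A 2-point error in the level does not overturn that. Nor can 89% simply be changed to 87% beside the 90%: that would create a 3-point drop which the Protocol never claimed, and the over-time correlation behind the 90% is not given.
- **That the endpoint is defined at the wrong threshold.** Sections 9.2.1 and 14.5.4 both say counts per half-minute, and nothing in the Protocol applies 1500 per minute. The fault is a table label.

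It also stands that the impact is small. Power of 87% is still above 80%, and calling the effect small is as true at 0.16 SD as at 0.17.

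**Conclusion.** The point holds as an internal contradiction in the primary power statement. For ICC 0.01, 120 girls invited and 20% refusal, the figure supported by Table 14.2 is 87%, not 89%: a type II risk of 13% rather than 11%. The contradiction between text and table needs no assumption. The recomputed 86.7% rests on the 80/20 blend; across the weightings tried, the same cell runs from about 82% to 92%. The blended 14.36 MET-minutes is therefore a reconstruction and not a value the Protocol states.

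The repeated 89% in A.4.6.1, the 14.5/86 ratio in A.4.6.2, the reference to Table 1 and the cpm label are secondary inconsistencies of the same editorial kind. The numerical inputs of Table 14.1, the number of schools and the number of girls all stand.

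**What to change.** 1. In 14.5.4, change 89% to 87% and cite Table 14.1 instead of Table 1.
2. In A.4.6.1, reconcile the 90%/89% pair with Table 14.2 and state the over-time correlation behind the 90%.
3. In A.4.6.2, replace 14.5/86=0.17 with 15.6/94.9=0.16.
4. In Table 14.1, change cpm to counts per half-minute in the mean and SD rows.
5. State the weighting of the 15.6 and 9.4 effects used for Table 14.2. This should come from the sponsor's own calculation; the 80/20 blend used here should not be inserted as if it were the Protocol's.

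The cost is text corrections, plus retrieving the correlation and the weighting from the sponsor's calculation. The stated power becomes 2 points less favorable, and the design and analysis do not change.
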